5.2.2.2. Treatment allocation to the subject

The treatment numbers will be allocated by dose.

5.2.2.2.1. Study group and treatment number allocation

The target will be to enroll ~470 eligible subjects who will be randomly assigned to 10 study groups in a (1:1:1:1:1:1:1:1:1:1) ratio (~47 subjects in each group).

Allocation of the subject to a study group at the investigator site will be performed using SBIR. The randomization algorithm will use a minimization procedure accounting for center, sex, age (18-30 years vs. 31-39 years) and history of influenza vaccination since the 2014/2015 season (yes vs. no). Minimization factors will have equal weight in the minimization algorithm.

After obtaining the signed and dated ICF from the subject and having checked the eligibility of the subject, the site staff in charge of the vaccine/product administration will access SBIR. Upon providing the subject identification number, the randomization system will determine the study group and will provide the treatment number to be used for the first dose.

The number of each administered treatment must be recorded in the eCRF on the Vaccine Administration screen.

When SBIR is not available, please refer to the SBIR user guide or the SPM for specific instructions.

5.2.2.2. *Treatment number allocation for subsequent doses*

For each dose subsequent to the first dose, the study staff in charge of the vaccine/product administration will access SBIR, provide the subject identification number, and the system will provide a treatment number consistent with the allocated study group.

The number of each administered treatment must be recorded in the eCRF on the Vaccine Administration screen.

5.3. *Method of blinding*

Data will be collected in an observer-blind manner. By observer-blind, it is meant that during the course of the study, the vaccines/products recipient and those responsible for the evaluation of any study endpoint (e.g. safety, reactogenicity) will all be unaware of which vaccine/product was administered. To do so, vaccine/product preparation and administration will be done by authorized medical personnel who will not participate in any of the study clinical evaluation assays.

The site staff will work in an observer-blind manner during the entire study. As the vaccines appearance and preparation are different, two teams of study personnel will be set up:

- A team of unblinded personnel (responsible for the reception, preparation and administration of the vaccines).
- A team of blinded personnel (responsible for the clinical safety evaluation of the subjects).

Please refer to the SPM for more information on vaccine preparation and administration while maintaining the blind.

An analysis of data collected up to Day 85 and Month 14 + 28 days will be done on as cleaned as possible data up to Visit 6 and Visit 10, respectively (refer to Section 10.11.1 for more information). At Day 85 analysis, the GSK statistician will be unblinded (i.e. will have access to the individual subject treatment assignment). The remaining GSK study personnel will stay blinded (i.e. will not have access to the individual subject treatment assignment) until study end. It is possible however, due to the limited sample size, that unblinding occurs for a few subjects having a specific adverse event (AE) or serious adverse event (SAE) (e.g. an AE/SAE occurring only in a single group). Therefore anyone having access to the analysis of Day 85 could become unblinded regarding those specific cases.

The laboratory in charge of the laboratory testing will be blinded to the treatment, and codes will be used to link the subject and study (without any link to the treatment attributed to the subject) to each sample.

5.4. General study aspects

Supplementary study conduct information not mandated to be present in this protocol is provided in the accompanying SPM. The SPM provides the investigator and the site personnel with administrative and detailed technical information that does not impact the safety of the subjects.

5.4.1. Independent data monitoring committee

An IDMC will be established by GSK Biologicals for the purpose of monitoring the study and to provide independent, non-binding advice on safety and ethics. The IDMC will provide recommendations about stopping, continuing or modifying the trial. Refer to Section 8.8 for a description of the holding rules and safety monitoring put in place for this study.

5.4.2. Influenza-like illness surveillance

ILI is defined as at least one of these systemic symptoms:

- Temperature (oral) $\geq 37.8^{\circ}\text{C}/98.6^{\circ}\text{F}$ and/or,
- Myalgia (widespread muscle ache);

AND at least one of these respiratory symptoms:

- Cough and/or,
- Sore throat.

All ILIs will be reported as unsolicited AEs or SAEs, as applicable.

Passive surveillance will be carried out from Visit 1 (after Dose 1) until the end of the study (Visit 12). All study participants will be instructed to contact the investigator/study staff in case they experience signs symptoms of ILI as defined above.

The investigator/study staff will schedule a visit for the collection of nasal and throat swab specimens preferably within 24 hours (but not later than 7 days) after the onset of the ILI. Refer to the SPM for a detailed description of the procedures.

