8.3.3.2. Assessment of adverse events

8.3.3.2.1. Assessment of intensity

The intensity of the following solicited AEs will be assessed as described:

Table 22 Intensity scales for solicited symptoms

Adverse Event	Intensity grade	Parameter
Pain at injection site	0	None
	1	Mild: Any pain neither interfering with nor preventing normal every day activities.
	2	Moderate: Painful when limb is moved and interferes with every day activities.
	3	Severe: Significant pain at rest. Prevents normal every day activities.
Redness at injection site		Record greatest surface diameter in mm
Swelling at injection site		Record greatest surface diameter in mm
Fever*		Record temperature in °C/°F
Headache	0	Normal
	1	Mild: Headache that is easily tolerated
	2	Moderate: Headache that interferes with normal activity
	3	Severe: Headache that prevents normal activity
Fatigue	0	Normal
	1	Mild: Fatigue that is easily tolerated
	2	Moderate: Fatigue that interferes with normal activity
	3	Severe: Fatigue that prevents normal activity
Gastrointestinal symptoms (nausea, vomiting, diarrhea and/or abdominal pain)	0	Normal
	1	Mild: Gastrointestinal symptoms that are easily tolerated
	2	Moderate: Gastrointestinal symptoms that interfere with normal activity
	3	Severe: Gastrointestinal symptoms that prevent normal activity
Arthralgia	0	Normal
	1	Easily tolerated
	2	Interferes with normal activity
	3	That prevents normal activity
Myalgia	0	Normal
	1	Easily tolerated
	2	Interferes with normal activity
	3	That prevents normal activity
Shivering	0	Normal
	1	Easily tolerated
	2	Interferes with normal activity
	3	That prevents normal activity

*Fever is defined as temperature $\geq 38.0^{\circ}\text{C} / 100.4^{\circ}\text{F}$. The preferred location for measuring temperature in this study will be the oral cavity.

The maximum intensity of local injection site redness/swelling/fever will be scored at GSK Biologicals as follows:

Redness/swelling	
0:	$\leq 20 \text{ mm}$
1:	$> 20 - \leq 50 \text{ mm}$
2:	$> 50 - \leq 100 \text{ mm}$
3:	$> 100 \text{ mm}$

Temperature $> 39^{\circ}\text{C}/102.2^{\circ}\text{F}$ will be considered as grade 3 fever.

The investigator will assess the maximum intensity that occurred over the duration of the event for all unsolicited AEs (including SAEs) recorded during the study. The assessment will be based on the investigator's clinical judgement.

The intensity should be assigned to one of the following categories:

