8.8.1. Holding rules

Study holding rules which will be applied during the safety evaluation are defined below.

If a holding rule 1a through 1d is observed by the investigator, it will be reported promptly to GSK within 24 hours. Meeting the other holding rules will be determined by IDMC review of safety data at regular intervals.

These holding rules have been written under the assumption that safety data of all subjects will be available. Therefore, the investigator will be requested to record safety data meeting the criteria of holding rules in the eCRF within 24 hours after reception of the data to ensure that all necessary information are available for IDMC reviews. If the data from all subjects are not available, the holding rules will be assessed on a pro-rata basis.

Upon meeting of any holding rules, further vaccination will be immediately put on hold pending safety review and consultation with the GSK Biologicals' Vaccine Safety Monitoring Board (VSMB), as appropriate.

GSK Biologicals' decision on whether to suspend, modify, or continue the conduct of the study on all groups or on selected groups will be communicated to the investigators, to CBER, and to the IRBs/IECs.

In case of a safety concern, the final responsibility to recommend whether or not the trial should be stopped permanently rests with the sponsor, after having considered all the safety information available. If the trial is stopped, a letter indicating the reasons for stopping the study will be sent to the IRBs/IECs via the investigator(s), and to CBER via GSK Biologicals.

Table 24 Study holding rules

Holding rules	Event	Number/percentage of subjects
1a	Death or any life-threatening SAE.	≥ 1
1b	Any SAE that cannot reasonably be attributed to a cause other than vaccination	≥ 1
1c	Any withdrawal from the study or withdrawal from study vaccine(s)/product(s) (by investigator or subject request) following a grade 3 AE that cannot reasonably be attributed to a cause other than vaccination.	≥ 1
1d	Any local or general solicited AE leading to hospitalization, or fever > 40°C (104°F) (oral route) that cannot reasonably be attributed to a cause other than vaccination, or necrosis at the injection site, within the 7-day (Days 1-7) post-vaccination period.	≥ 1
2a	Any grade 3 solicited local AE lasting 48h or more in an investigational group, within the 7-day (Days 1-7) post-vaccination period.	≥ 30% (and ≥ 2 subjects in one group)

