10.8. Analysis of safety

The analysis will be performed on the ES.

All analyses will be descriptive. Data will be presented by dose, overall/dose and overall/subject. Outputs will be presented by study group. Analyses will be repeated pooling groups according to the adjuvant (AS01, AS03, no adjuvant).

- The percentage of subjects with at least one local AE (solicited and unsolicited), with at least one general AE (solicited and unsolicited) and with any AE during the solicited follow-up period will be tabulated with exact 95% CI. The same calculations will be performed for AEs rated as grade 3.
- The percentage of subjects reporting each individual solicited local and general AE during the solicited follow-up period will be tabulated with exact 95% CI. The same tabulation will be performed for grade 3 AEs and for AEs with relationship to vaccination.
- The verbatim reports of unsolicited AEs will be reviewed by a physician and the signs and AEs will be coded according to the Medical Dictionary for Regulatory Activities (MedDRA). The percentage of subjects with at least one report of unsolicited AE classified by the MedDRA and reported up to 28 days after vaccination will be tabulated with exact 95% CI. The same tabulation will be performed for grade 3 unsolicited AEs and for unsolicited AEs with a relationship to vaccination.
- The percentage of subjects with MAE(s) will be summarized by group with exact 95% CI.
- The percentage of subjects with episode(s) of ILI will be summarized by group with exact 95% CI. **(Amended: 11 July 2019)**
- At each hematology/biochemistry sampling timepoint, by study group, individual hematological and biochemical values will be presented as number of subjects out of range (above and below normal range) and tabulated by toxicity grading (refer to [APPENDIX C](#)). In addition, changes from baseline (median/interquartile range) will be presented.
- SAEs and pIMDs will be described in detail. Withdrawals due to (S)AEs will also be summarized.

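### The influenza-like-illness temperature criterion pairs 37.8 °C with 98.6 °F, which are 0.8 °C apart, so borderline case status depends on the unit used

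*Protocol*

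**What the plan says.** Protocol Section 5.4.2 defines ILI as at least one of two systemic symptoms, raised oral temperature or myalgia, and then adds "AND at least one of these respiratory symptoms", namely cough or sore throat. The temperature limb reads "Temperature (oral) $\geq 37.8^{\circ}\text{C}/98.6^{\circ}\text{F}$ and/or". The same pair of values stands in the synopsis, in the glossary entry for ILI and in the ILI surveillance item of Section 3. Nothing in the protocol corrects the pair or says which unit governs.

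The definition is put to use in several places:
- Subjects are told to contact the site when they have ILI symptoms, and a swab visit follows (Sections 5.4.2 and 5.6.14).
- Every ILI from Dose 1 to Month 26 is entered on an ILI screen and also as an adverse event (AE) or serious adverse event (SAE), whatever its intensity (Section 8.3.1).
- Section 10.8 plans this output: "The percentage of subjects with episode(s) of ILI will be summarized by group with exact 95% CI".

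Both temperature scales are admitted for recording. The intensity table in Section 8.3.3.2.1 has "Record temperature in °C/°F" for fever.

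**The concern.** A case definition has to classify the same patient the same way at every site. Here a site or subject working in Celsius applies one limit, and one working in Fahrenheit applies a lower one. On the Fahrenheit reading, a sore throat or cough with a temperature of 98.6 °F (37.0 °C) is already an ILI. On the Celsius reading it is not.

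The clinical definition carries more weight since Amendment 4. The endpoint of RT-PCR-confirmed influenza was removed, and swabs are now tested only where judged necessary and otherwise stored (Section 5.7.3). No planned laboratory-confirmed count remains to separate influenza from non-specific respiratory complaints. The ILI percentage therefore rests on the clinical definition alone.

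**Working it through.** **Inputs**
- ILI limit: 37.8 °C and 98.6 °F (synopsis, glossary, Sections 3 and 5.4.2).
- Comparison pairs: fever, 38.0 °C and 100.4 °F (Section 8.3.3.2.1); grade 3 fever, "Temperature $> 39^{\circ}\text{C}/102.2^{\circ}\text{F}$ will be considered as grade 3 fever" (same section); holding rule 1d, 40 °C and 104 °F (Section 8.8.1).

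**Formulas:** F = C × 9/5 + 32 and C = (F − 32) × 5/9.

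**ILI pair**
- 37.8 × 9/5 + 32 = 68.04 + 32 = 100.04 °F. The stated 98.6 °F is not reproduced.
- (98.6 − 32) × 5/9 = 66.6 × 5/9 = 37.0 °C. The stated 37.8 °C is not reproduced.
- Gap: 37.8 − 37.0 = 0.8 °C, or 100.04 − 98.6 = 1.44 °F.

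**Comparison pairs**
- 38.0 × 9/5 + 32 = 100.4 °F: agrees.
- 39 × 9/5 + 32 = 102.2 °F: agrees.
- 40 × 9/5 + 32 = 104 °F: agrees.

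The protocol's fever pairs convert exactly, so a difference of 1.44 °F is not rounding. The ILI pair is the same in all four places, so an error in reading the PDF is not a plausible explanation.

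**Who is reclassified**

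| Respiratory symptom | Myalgia | Oral temperature | Status depends on unit? |
|---|---|---|---|
| No | either | any | No: never ILI |
| Yes | Yes | any | No: always ILI |
| Yes | No | below 37.0 °C | No: never ILI |
| Yes | No | 37.0 °C to below 37.8 °C | **Yes** |
| Yes | No | 37.8 °C or above | No: always ILI |

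Only the fourth row is affected (98.6 °F to below 100.04 °F). The protocol gives neither the share of sites using each unit nor the expected frequency of such episodes, so no count can be derived.

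**What the fourth row feeds**
- *ILI percentage (Section 10.8):* directly exposed.
- *Unsolicited AEs:* Section 8.3.1 requires every AE starting within 28 days of a dose to be recorded regardless of intensity. A new cough or sore throat in that window is therefore recorded whether or not it is called an ILI. The endpoint in Section 10.1 and the tabulation in Section 10.8 cover that window only. ILI records beyond it do depend on the threshold but do not enter that tabulation.
- *Tests, sample size, holding rules:* none is defined on ILI (Sections 8.8.1, 10.4 and 10.9).

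**The case against.** The conversion error cannot be disputed; its importance can. ILI is not among the primary, secondary or tertiary endpoints in Sections 10.1 to 10.3. It yields one descriptive percentage per group. The affected band is narrow, and because the unit used at each site is not given, variation between sites is possible rather than shown. The sponsor had also stopped development of the vaccine by the time of Amendment 4. All of this stands, and it lowers the rating. None of it makes the two limits agree, and subjects were still to be followed to Month 26.

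Three stronger readings are tempting, and the protocol does not support them.

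- *Unsolicited AE counts are inflated.* A reader might infer this because every ILI must be recorded as an AE. The 28-day recording rule and the 28-day tabulation window leave the planned unsolicited AE percentage almost untouched.
- *Comparisons between groups are biased.* Allocation is minimised on center (Section 5.2.2.2.1) and assessment is observer-blind (Section 5.3), so unit-driven misclassification should fall roughly evenly on the ten groups. Some dilution of a real ILI difference is possible, but it cannot be quantified.
- *Surveillance for enhanced respiratory disease is undermined.* Section 1.3.1 says this is not considered a potential safety risk in the study, although it does offer ILI surveillance in response. The same section has the independent committee monitor all respiratory illness, which does not depend on the ILI limit. The Fahrenheit reading also misses no case that the Celsius reading would catch.

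**Conclusion.** The point holds in limited form. The criterion contradicts itself by 0.8 °C (1.44 °F) in every current statement of the definition. The contradiction decides ILI status, the swab visit and ILI recording for subjects with cough or sore throat, no myalgia and an oral temperature from 37.0 °C to below 37.8 °C. The exposed result is the descriptive ILI percentage by group. It can vary by site, and it can be inflated if the Celsius limit is taken as the reference; if the Fahrenheit limit was meant, sites using Celsius would under-report instead. The protocol does not settle which was intended.

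The arithmetic needs no assumption. The practical effect assumes that both units were in fact used to apply the definition. The protocol allows both for recording fever but does not document how sites applied the ILI limit. Severity: a worthwhile, cheap correction, not one on which the trial's conclusions depend.

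**What to change.** 1. The sponsor should reconcile the two limits and state which was intended. One threshold with its matching conversion should then stand in the synopsis, the glossary, Section 3 and Section 5.4.2, and on the diary cards, eCRF guidance and other site- and subject-facing materials.
2. Where a numeric temperature was recorded for an ILI episode, derive ILI status in the analysis by applying one limit to all sites, together with myalgia, cough and sore throat. This is conditional: Section 5.6.14 promises the onset date, the signs and symptoms and the swab date, but not explicitly a temperature value.
3. State the limit of this derivation in the report. The higher limit can be applied uniformly to reported episodes. The lower one cannot be fully applied, because episodes below 37.8 °C that were never reported under the Celsius reading cannot be recovered. This favours correcting the text promptly.

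The cost is a text correction, a memo to sites and one derived variable. No sample-size or testing provision changes.

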5.5. Outline of study procedures

The list of study procedures is presented in [Table 5](#) for Phase I subjects and in [Table 6](#) for Phase II subjects.

Table 5 List of study procedures for Phase I subjects (Amended: 11 July 2019)

Epoch	Screening	Primary							Booster				In case of ILI**
		Visit 1	Visit 2	Visit 3	Visit 4	Visit 5	Visit 6	Visit 7	Visit 8	Visit 9	Visit 10	Visit 11	Visit 12
Type of contact	Screening Visit*												
Timepoints	Pre-Day 1	Day 1	Day 8	Day 29	Day 57	Day 64	Day 85	M8	M14	M14+7D	M14+28D	M20	M26
Sampling timepoints	Screening	PRE	P1d7	P1d28	P1d56	P1d7	P1d28	M8	M14	P11d7	P11d28	M20	M26
Informed consent	•												
Check inclusion/exclusion criteria	•	0											
Collect demographic data	•												
Medical history	0	•											
History of influenza vaccination within previous 3 seasons (2014/2015, 2015/2016, 2016/2017)	•												
Physical examination	•	•	0	0	0	0	0	0	0	0	0	0	0
Pregnancy test §	•	•			•				•				
Check contraindications and warnings and precautions to vaccination		0			0				0				
Pre-vaccination body temperature		•			•				•				
Measure/record height and weight	•												
Vaccine													
Study group and treatment number allocation		0											
Treatment number allocation for subsequent doses					0				0				
Recording of administered treatment number		•			•				•				
Vaccine administration		•†			•†				•†				
60 minutes post-vaccination observation		0			0				0				
Laboratory assays													
Blood sampling for antibody determination (~12 mL)		•		•		•		•	•	•	•	•	•
Blood sampling for hematology/biochemical analysis (~5.5 mL)	•	•‡	•	•	•	•	•	•	•	•	•	•	•

CONFIDENTIAL

207543 (FLU D-SUV-ADJ-001)

Protocol Amendment 4 Final

Epoch	Screening	Primary							Booster				In case of ILI**	
Type of contact	Screening Visit*	Visit 1	Visit 2	Visit 3	Visit 4	Visit 5	Visit 6	Visit 7	Visit 8	Visit 9	Visit 10	Visit 11	Visit 12	
Timepoints	Pre-Day 1	Day 1	Day 8	Day 29	Day 57	Day 64	Day 85	M8	M14	M14+7D	M14+28D	M20	M26	
Sampling timepoints	Screening	PRE	Pld7	Pld28	Pld56	Plld7	Plld28	M8	M14	Pllld7	Pllld28	M20	M26	
Blood sampling for passive transfer (~2.5 mL)		●					●		●					
Nasal and throat swab sampling														
ILI surveillance														
Surveillance for ILI		0	0	0	0	0	0	0	0	0	0	0	0	
Documentation of symptoms and signs of ILI		●	●	●	●	●	●	●	●	●	●	●	●	
Safety assessments														
Record any concomitant medications/vaccinations	●	●	●	●	●	●	●	●	●	●	●	●	●	
Record any intercurrent medical conditions		●	●	●	●	●	●	●	●	●	●	●	●	
Distribution of diary cards ¹	0		0	0		0	0	0		0	0	0	0	
Recording of solicited AEs within 7 days post-vaccination		●	●		●	●			●	●				
Recording of unsolicited AEs within 28 days post-vaccination		●	●	●	●	●	●		●	●	●			
Recording of ILIs as unsolicited AEs/SAE, as applicable		●	●	●	●	●	●	●	●	●	●	●	●	
Return of diary cards		0	0	0	0	0	0	0	0	0	0	0	0	
Diary card transcription by investigator		●	●	●	●	●	●	●	●	●	●	●	●	
Recording of AEs and SAEs leading to withdrawal from the study		●	●	●	●	●	●	●	●	●	●	●	●	
Recording of SAEs, MAEs, pIMDs and pregnancies		●	●	●	●	●	●	●	●	●	●	●	●	
Recording of SAEs related to study participation, or to a concurrent GSK medication/vaccine	●	●	●	●	●	●	●	●	●	●	●	●	●	
Screening conclusion	●													
Study conclusion													●	

Note: the double-line border following Day 85 and Month 14 + 28 days indicates the analyses which will be performed on all data (i.e. data that are as clean as possible) obtained up to Day 85 and Month 14 + 28 days, respectively.

D = day; M = month (= 28 days); PRE = pre-vaccination; PI = post-dose 1; PII = post-dose 2; PIII = post-dose 3 (booster)

AE = adverse events, ILI = influenza-like illness; SAE = serious adverse event; MAE = medically attended event; pIMD = potential immune-mediated disease

● is used to indicate a study procedure that requires documentation in the individual eCRF

CONFIDENTIAL

207543 (FLU D-SUV-ADJ-001)
Protocol Amendment 4 Final

○ is used to indicate a study procedure that does not require documentation in the individual eCRF

* Screening evaluations may be completed 2 to 28 days before Day 1. Site staff should allow sufficient time between the Screening and Visit 1 to receive and review screening safety laboratory test results. If a delay occurs such that the interval between Screening and the Visit 1 vaccination exceeds 28 days, a re-screening visit should be scheduled before Visit 1 during which blood sample collection for safety laboratory assessment must be repeated; an interim medical history and physical examination must be obtained and inclusion / exclusion criteria must be re-reviewed. Only data from the re-screening visit, if it occurs, will be recorded in the eCRF and taken into consideration.

** This visit is only applicable following passive surveillance contacts for subjects with ILI (see Section 5.4.2).

§ Only for females subjects of childbearing potential. An urine pregnancy test will be performed. A serum pregnancy test instead of a urine pregnancy test should only be considered if required by local or ethics committee regulations. If a serum pregnancy test instead of a urine pregnancy test is required by country, local or ethics committee regulations, a blood sample will be collected from women of childbearing potential at these visits and will be used for the test as per local guidance. The results must be obtained and be confirmed negative before vaccination.

† Blood samples must be taken before vaccine administration

‡ Blood sample for hematology/biochemical assessment will not be drawn at Visit 1 if this visit occurs less than one week after the screening visit

1 Diary cards will allow the collection of solicited and unsolicited symptoms, concomitant medications/vaccinations, MAEs and episode(s) of ILI. Refer to the SPM for more details on the usage of the diary cards.

Table 6 List of study procedures for Phase II subjects (Amended: 11 July 2019)

Epoch	Primary						Booster						In case of ILI *
	Visit 1	Visit 2	Visit 3	Visit 4	Visit 5	Visit 6	Visit 7	Visit 8	Visit 9	Visit 10	Visit 11	Visit 12	
Type of contact	Visit 1	Visit 2	Visit 3	Visit 4	Visit 5	Visit 6	Visit 7	Visit 8	Visit 9	Visit 10	Visit 11	Visit 12	
Timepoints	Day 1	Day 8	Day 29	Day 57	Day 64	Day 85	M8	M14	M14+7D	M14+28D	M20	M26	
Sampling timepoints	PRE	PId7	Pld28	Pld56	PIld7	PIld28	M8	M14	PIld7	PIld28	M20	M26	
Informed consent	●												
Check inclusion/exclusion criteria	●												
Collect demographic data	●												
Medical history	●												
History of influenza vaccination within previous 3 seasons (2014/2015, 2015/2016, 2016/2017)	●												
Physical examination	●	0	0	0	0	0	0	0	0	0	0	0	
Pregnancy test §	●			●				●					
Check contraindications and warnings and precautions to vaccination	0			0				0					
Pre-vaccination body temperature	●			●				●					
Measure/record height and weight	●												
Vaccine													
Study group and treatment number allocation	0												
Treatment number allocation for subsequent doses				0				0					
Recording of administered treatment number	●			●				●					
Vaccine administration	●†			●†				●†					
30 minutes post-vaccination observation	0			0				0					
Laboratory assays													
Blood sampling for antibody determination (~12 mL)	●		●		●		●	●	●	●	●	●	
Blood sampling for CMI response (~40 mL) #	●	●	●		●	●	●	●	●	●			
Blood sampling for hematology/biochemical analysis (~5.5 mL)	●	●	●	●	●	●	●	●	●	●	●	●	
Blood sampling for passive transfer (~2.5 mL)	●					●		●					
Nasal and throat swab sampling													●

CONFIDENTIAL

207543 (FLU D-SUV-ADJ-001)

Protocol Amendment 4 Final

Epoch	Primary						Booster					In case of ILI *	
	Visit 1	Visit 2	Visit 3	Visit 4	Visit 5	Visit 6	Visit 7	Visit 8	Visit 9	Visit 10	Visit 11	Visit 12	
Type of contact	Visit 1	Visit 2	Visit 3	Visit 4	Visit 5	Visit 6	Visit 7	Visit 8	Visit 9	Visit 10	Visit 11	Visit 12	
Timepoints	Day 1	Day 8	Day 29	Day 57	Day 64	Day 85	M8	M14	M14+7D	M14+28D	M20	M26	
Sampling timepoints	PRE	P1d7	P1d28	P1d56	P1d7	P1d28	M8	M14	P1d7	P1d28	M20	M26	
ILI surveillance													
Surveillance for ILI	0	0	0	0	0	0	0	0	0	0	0	0	
Documentation of symptoms and signs of ILI	●	●	●	●	●	●	●	●	●	●	●	●	
Safety assessments													
Record any concomitant medications/vaccinations	●	●	●	●	●	●	●	●	●	●	●	●	
Record any intercurrent medical conditions	●	●	●	●	●	●	●	●	●	●	●	●	
Distribution of diary cards ¹	0		0	0		0	0	0		0	0		
Recording of solicited AEs within 7 days post-vaccination	●	●		●	●			●	●				
Recording of unsolicited AEs within 28 days post-vaccination	●	●	●	●	●	●		●	●	●			
Recording of ILIs as unsolicited AEs/SAE, as applicable	●	●	●	●	●	●	●	●	●	●	●	●	
Return of diary cards		0	0	0	0	0	0	0	0	0	0	0	
Diary card transcription by investigator		●	●	●	●	●	●	●	●	●	●	●	
Recording of AEs and SAEs leading to withdrawal from the study	●	●	●	●	●	●	●	●	●	●	●	●	
Recording of SAEs, MAEs, pIMDs and pregnancies	●	●	●	●	●	●	●	●	●	●	●	●	
Recording of SAEs related to study participation, or to a concurrent GSK medication/vaccine	●	●	●	●	●	●	●	●	●	●	●	●	
Study conclusion												●	

Note: the double-line border following Day 85 and Month 14 + 28 days indicates the analyses which will be performed on all data (i.e. data that are as clean as possible) obtained up to Day 85 and Month 14 + 28 days, respectively.

D = day; M = month (= 28 days); PRE = pre-vaccination; PI = post-dose 1; PII = post-dose 2; PIII = post-dose 3 (booster)

CMI = cell-mediated immunity; AE = adverse events; ILI = influenza-like illness; SAE = serious adverse event; MAE = medically attended event; pIMD = potential immune-mediated disease

● is used to indicate a study procedure that requires documentation in the individual eCRF

○ is used to indicate a study procedure that does not require documentation in the individual eCRF

* This visit is only applicable following passive surveillance contacts for subjects with ILI (see Section 5.4.2).

CONFIDENTIAL

207543 (FLU D-SUV-ADJ-001)

Protocol Amendment 4 Final

§ Only for females subjects of childbearing potential. An urine pregnancy test will be performed. A serum pregnancy test instead of a urine pregnancy test should only be considered if required by local or ethics committee regulations. If a serum pregnancy test instead of a urine pregnancy test is required by country, local or ethics committee regulations, a blood sample will be collected from women of childbearing potential at these visits and will be used for the test as per local guidance. The results must be obtained and be confirmed negative before vaccination.

† Blood samples must be taken before vaccine administration

Only for subjects included in the CMI sub-cohort

1 Diary cards will allow the collection of solicited and unsolicited symptoms, concomitant medications/vaccinations, MAEs and episode(s) of ILI. Refer to the SPM for more details on the usage of the diary cards.

Whenever possible, the investigator should arrange study visits within the interval described in [Table 7](#).

Table 7 Intervals between study visits

Interval	Optimal length of interval	Allowed interval**
Screening to Visit 1*	2-28 days	
Visit 1 → Visit 2	7 days	7-9 days
Visit 1 → Visit 3	28 days	28-38 days
Visit 1 → Visit 4	56 days	56-66 days
Visit 4 → Visit 5	7 days	7-9 days
Visit 4 → Visit 6	28 days	28-38 days
Visit 4 → Visit 7	168 days	168-196 days
Visit 4 → Visit 8	336 days	336-364 days
Visit 8 → Visit 9	7 days	7-9 days
Visit 8 → Visit 10	28 days	28-38 days
Visit 8 → Visit 11	168 days	168-196 days
Visit 8 → Visit 12	336 days	336-364 days

*Only applicable for Phase I subjects. Screening evaluations may be completed 2 to 28 days before Day 1. Site staff should allow sufficient time between the screening and Day 1 visits to receive and review screening safety laboratory test results. If a delay occurs such that the interval between screening and the Day 1 vaccination exceeds 28 days, a re-screening visit should be scheduled before Visit 1.

**Visits out of the allowed interval can lead to elimination from the Per-Protocol set for immunogenicity analysis.

